7.3.6 UNSCHEDULED VISIT

Unscheduled visits may be related but not limited to development of TKI toxicities. In that case the Grade of toxicity will be documented and the medication dose will be adjusted as per protocol (See section 6.1.8, and Appendix 3). All unscheduled visit will be documented in the patients chart.

7.3.7 SCHEDULE OF EVENTS TABLE

Table 8. Schedule of events

Phase	Screen	Experimental phase																	
		1	1	1	1	2	2	3	4	5	6	9	12	16	20	24	EOT ⁿ		
Cycle (28 days) ^a	0	1	1	1	1	2	2	3	4	5	6	9	12	16	20	24	EOT ⁿ		
Day ^b	-28 to -0	1	8	15	22	1	15	1	1	1	1	1	1	1	1	1	30		
Assessments																			
Informed consent ^c	X ^d	X ^d																	
Inclusion/exclusion	X ^d	X ^d																	
Randomization		When/if tumor marker drops ≥50% within first 2 cycles ^m																	
Demographic data	X ^d	X ^d																	
pTNM staging ^e	X ^d	X ^d																	
Medical history	X ^d	X ^d																	
ECOG ^f	X ^d	X ^d	X	X	X	X	X	X	Patients on conventional therapy: Q3 cycles (Day 1 of cycles 6, 9, 12, 15, 18, 21, 24)									X	
Vital signs ^g	X ^d	X ^d	X	X	X	X	X	X	Patients in the adaptive therapy: On TKI: Every day 1 of each cycle for up to 12 cycles, Q2 cycles (Day 1 of cycles 14, 16, 18, 20, 22 and 24). Off TKI: Every day 1 of each cycle until resume TKI.									X	
Physical exam	X ^d	X ^d	X	X	X	X	X	X										X	
Laboratory tests ^h	X ^d	X ^d	X	X	X	X	X	X	X	X	X	X	X	X	X	X	X	X	
Urine dipstick	X ^d	X ^d	X	X	X	X	X	X	X	X	X	X	X	X	X	X	X	X	
Thyroid panel ⁱ	X ^d	X ^d		X			X	X	X	Patients on conventional therapy: Q3 cycles (Day 1 of cycles 6, 9, 12, 15, 18, 21, 24) Patients in the adaptive therapy: Day 1 of each cycle									X
Pregnancy test ^l	X ^d	X ^d																	
Imaging studies (CT/MRI) ^k	X ^d	X ^d							X			X	X	X	X	X	X		
Mandatory research blood collection	X								X			X	X	X			X	X	
Tumor collection	Mandatory: - Archival Optional: - Fresh Tissue																	Optional: - Fresh Tissue	
Concomitant meds	X	Throughout																X	
AEs/SAEs ^l		Throughout																X	
Survival		Throughout																X	

- a: Patients in adaptive therapy arm will continue to follow the schedule with TKI withheld as long as their markers continue to be below 70% of the 'baseline' level. Upon resumption of TKI therapy the Cycle number will match that which would be expected based on duration on treatment (ie TKI therapy is omitted, not held).
- b: Efforts should be made to conduct study visits on the day scheduled during the first month (\pm 3 days) and there after \pm 5 days. Clinical laboratory assessments may be conducted anytime within 72 hours prior to the scheduled visit, unless otherwise specified in the Schedule of Visits and Procedures.
- c: Informed consent may be taken up to 8 weeks prior to C1D1.
- d: The baseline assessment can be performed on Cycle 1 Day (C1D1), prior to treatment. Clinical and laboratory assessments are valid if obtained within 72 hours of baseline assessment.
- e: For pTNM Staging see Appendix 1
- f: For ECOG assessments see Appendix 2.
- g: Assessments will include vital signs (resting BP, HR, RR, and body temperature, weight, and height. Height will be measured at the Screening Visit only. Elevated BP (Systolic BP \geq 140 mmHg and/or elevated Diastolic BP \geq 90 mmHg) should be confirmed by 2 assessments 1 hour apart. If systolic BP is \geq 160 mmHg or diastolic BP \geq 100 mmHg, BP should be confirmed by repeat measurements after an hour.
- h: Laboratory tests include: CBC w/differential, CMP, ALT, AST, magnesium, amylase, lipase, urine dipstick and if clinically indicated INR (see Table 6).
- i: Thyroid panel includes: TSH, free T4, and for patients with DTC thyroglobulin and thyroglobulin antibodies; and for patients with MTC calcitonin and CEA (see Table 6). Thyroid panel results may be collected up to 7 days prior to the first dose on Cycle 1 Day 1. These lab tests should be performed while the patient is in a fasting state.
- j: Serum or urine, in women of childbearing potential only.
- k: Baseline imagine to include CT/MRI of head /neck/chest/abdomen/pelvis and other areas of known disease. On treatment imagine will include only areas of known disease plus any areas of newly suspected disease.
- l: AEs/SAEs will be assessed during each visit clinically and based on laboratory data. Patients will be encouraged to report AEs/SAEs at the earliest recognition via the phone between the visits.
- m: Includes the analysis on Cycle 3, day 1. Only a decrease in tumor markers that met inclusion criteria at baseline may be used for randomization purposes.
- n: End of Treatment visit is to occur 30 days after the last dose of TKI therapy (or within 30 days of being removed from treatment in the case of adaptive therapy patients) \pm 7 days. The optional research biopsy may be taken up to 30 days after this visit as scheduling may require. If the subject is unable or unwilling to return to clinic this visit can be conducted via a telephone call.

7.4 CONCOMITANT MEDICATIONS, TREATMENTS, AND PROCEDURES

All concomitant prescription medications, over-the-counter medications, and non-prescription medications taken during study participation will be recorded on the case report forms (CRFs). All additional local therapies for metastatic lesions (including, but not limited to EBRT, surgery, embolization, ethanol injections, etc.) will be recorded on CRFs.

7.5 PROHIBITED MEDICATIONS, TREATMENTS, AND PROCEDURES

Due to its common use and interference with many thyroid hormone and biomarker assays including thyroglobulin, patients will not be allowed to take supplemental biotin in any form.

For patients treated with Lenvatinib, Sorafenib, Cabozantinib, or Vandetanib treatment, the following concomitant medications will not be permitted unless discussed with, and approved by the clinical instigators.

Lenvatinib: No medications are contraindicated.

- No dose adjustment of LENVIMA is recommended when co-administered with CYP3A, P-glycoprotein (P-gp), and breast cancer resistance protein (BCRP) inhibitors and CYP3A and P-gp inducers.

Sorafenib: Sorafenib in combination with carboplatin/paclitaxel is contraindicated in patients with squamous cell lung cancer. In combination with gemcitabine/cisplatin is not recommended in patients with squamous cell lung cancer

- Avoid concomitant use of strong CYP3A4 inducers (such as, carbamazepine, dexamethasone, phenobarbital, phenytoin, rifampin, rifabutin, St. John's wort), when possible, because these drugs can decrease the systemic exposure to Sorafenib.

Cabozantinib: No medications are contraindicated.

- Avoid taking a strong CYP3A4 inhibitor (e.g., ketoconazole, itraconazole, clarithromycin, atazanavir, indinavir, nefazodone, nelfinavir, ritonavir, saquinavir, telithromycin, voriconazole) while taking Cabozantinib or reduce the dosage of Cabozantinib if concomitant use with strong CYP3A4 inhibitors cannot be avoided (see section 6.1.8).
- Avoid ingestion of foods (e.g., grapefruit, grapefruit juice) or nutritional supplements that are known to inhibit cytochrome P450 while taking Cabozantinib.
- Avoid chronic co-administration of strong CYP3A4 inducers (e.g., phenytoin, carbamazepine, rifampin, rifabutin, rifapentine, phenobarbital, St. John's Wort) with Cabozantinib or increase the dosage of Cabozantinib if concomitant use with strong CYP3A4 inducers cannot be avoided.
- Concomitant administration of MRP2 inhibitors may increase the exposure to cabozantinib. Monitor patients for increased toxicity when MRP2 inhibitors (e.g., abacavir, adefovir, cidofovir, furosemide, lamivudine, nevirapine, ritonavir, probenecid, saquinavir, and tenofovir) are coadministered with Cabozantinib.

Vandetanib: No medications are contraindicated.

- Avoid administration of Vandetanib with anti-arrhythmic drugs (including but not limited to amiodarone, disopyramide, procainamide, sotalol, dofetilide) and other drugs that may prolong the QT interval (including but not limited to chloroquine, clarithromycin, dolasetron, granisetron, haloperidol, methadone, moxifloxacin, and pimozide).
- Avoid concomitant use of known strong CYP3A4 inducers during Vandetanib therapy. Avoid concomitant use of St. John's Wort because it can decrease Vandetanib exposure unpredictably.
- Use caution and closely monitor for toxicities when administering Vandetanib with drugs that are transported by OCT2 like metformin.
- Use caution and closely monitor for toxicities when administering CAPRELSA with digoxin

7.6 PROPHYLACTIC MEDICATIONS, TREATMENTS, AND PROCEDURES

Most common adverse events of Lenvatinib, Sorafenib, Cabozantinib, or Vandetanib therapy will be discussed in detail with the study participant on enrollment/baseline visit. Early recognition and early management of adverse events will be emphasized. The study participant will be provided with the information on the preventive strategies for most common adverse events of TKI therapy.

7.7 RESCUE MEDICATIONS, TREATMENTS, AND PROCEDURES

Acute toxicities will be managed as described above in the "dose adjustments / modifications/ delays" section of this protocol.

7.8 PARTICIPANT ACCESS TO STUDY AGENT AT STUDY CLOSURE

Lenvatinib and Sorafenib, and Cabozantinib and Vandetanib are FDA approved drugs for treatment of progressive metastatic RAI refractory differentiated thyroid cancer and medullary thyroid cancer, respectively. Study participant will receive the medication as per standard of care if indicated upon study closure.

8. ASSESSMENT OF SAFETY

8.1 SPECIFICATION OF SAFETY PARAMETERS

Study participants will be monitored closely based on clinical, laboratory and imaging studies as outlined in study calendar (Table 8). Lenvatinib, Sorafenib, Cabozantinib and Vandetanib AEs and SAEs have been well described in literature (9-12). Patients will be educated and encouraged to report any AEs and SAEs promptly. Our primary endpoints include evaluation of safety and toxicity of adaptive TKI therapy and its comparison to conventional TKI therapy by measuring incidence of AEs and SAEs and time to its developments in adaptive and conventional therapy arms.

All AEs and SAEs will be graded according to CTCAE v5.0 (Appendix 3) and recorded in patient's charts and CRFs.

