4. STUDY DESIGN AND ENDPOINTS

4.1 DESCRIPTION OF THE STUDY DESIGN

This is a pilot randomized phase 2 clinical trial to evaluate the efficacy and tolerability of TKI therapy through adaptive (intermittent) versus conventional (continuous) regimen in patients with DTC or MTC. Eligible subjects with DTC or MTC will have measurable disease according to Response Evaluation Criteria in Solid Tumors (RECIST 1.1) and will be randomized 2 to 1 to receive adaptive (intermittent) versus conventional (continuous) therapy when and if the tumor marker drops 50% or more from the baseline level (before initiating TKI treatment) within the first two months of treatment. Randomization will be stratified by cancer types, DTC vs. MTC. Patients in which the tumor marker does not drop by 50% or more within 2 months (“non-responders”) will be kept on conventional therapy and used to compare with the patients who drop their tumor markers by 50% or more as an exploratory analysis.

All patients will start receiving standard of care treatments: Lenvatinib 24 mg daily or Sorafenib 400 mg twice daily with DTC; Cabozantinib 140 mg daily or Vandetanib 300 mg daily with MTC. Doses will be adjusted as needed due to toxicity or drug tolerance in both arms (See section 6.1.8).

- Patients in the conventional therapy regimen (“responders” and non-responders”) will receive continuous (daily) treatment at the indicated dose.

- Patients in the adaptive therapy regimen will receive TKI therapy in cycles: continuous (daily) treatment at the indicated dose until the patients’ tumor marker (thyroglobulin in DTC patients; calcitonin or CEA in MTC patients) drops by $\geq 50\%$ from the level at the time of enrollment (“baseline” level). $\geq 70\%$ of Only tumor markers that meet inclusion criteria at baseline can be used for randomization and adaptive therapy purposes. A new cycle of TKI treatment will begin:

1. When/if the tumor marker increases to $\geq 70\%$ of the “baseline” level.
OR
2. At the discretion of the treating physician, if a patient develops worsening disease-related symptoms with rising tumor marker levels indicating disease progression. In the case of resumption for disease-related symptoms, TKI treatment will continue until the symptoms improve at the discretion of the treating physician and the tumor markers are again $\leq 50\%$ from the level at the time of enrollment.

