6.1.8 DOSE ADJUSTMENTS/MODIFICATIONS/DELAYS

All patients will start receiving standard of care treatment:

- DTC: Lenvatinib 24 mg daily or Sorafenib 400 mg twice daily
- MTC: Cabozantinib 140 mg daily or Vandetanib 300 mg daily.

Dose will be adjusted as needed due to toxicity or drug tolerance in both arms (See below).

- Patients in the conventional therapy regimen (“responders” and non-responders”) will receive continuous (daily) treatment at the indicated dose.

- Patients in the adaptive therapy regimen will receive TKI therapy in cycles: continuous (daily) treatment at the indicated dose until the patients’ tumor marker (thyroglobulin in DTC patients; calcitonin or CEA in MTC patients) drops by $\geq 50\%$ from the level at the time of enrollment (“baseline” level). Only tumor markers that meet inclusion criteria at baseline can be used for randomization and adaptive therapy purposes. A new cycle of TKI treatment will begin:

1. When/if the tumor marker increases to $\geq 70\%$ of the “baseline” level.

OR

2. At the discretion of the treating physician if a patient develops worsening disease-related symptoms with rising tumor marker levels indicating disease progression. In the case of resumption for disease-related symptoms, TKI treatment will continue until the symptoms improve at the discretion of the treating physician and the tumor markers are again $\leq 50\%$ from the level at the time of enrollment.

All study participants will continue to receive treatment until confirmed disease progression, development of unacceptable toxicity, withdrawal of consent, or study termination by investigator.

After disease progression subjects will be followed for survival and may be treated according to standards of care, which includes conventional (continuous) TKI treatment for patients in the adaptive therapy arm.

Held doses will be considered missed and will not be made up so that patients will complete on-study treatment within the anticipated 24 month duration. Treatment may be delayed for toxicity, other palliative treatments (i.e. palliative radiation, palliative surgery, etc.) for a maximum of 4 weeks. Any treatment beyond the 24 months specified herein will be considered off protocol and not subject to the requirements of this protocol.

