7.3.3 FOLLOW-UP

Follow-up Visits

Study participants will be seen weekly for the first cycle (Cycle 1 Days 8, 15 and 22), every two weeks for the second cycle (Cycle 2 Days 1, 15), every four weeks until cycle 12 (Day 1 of Cycles 3-12); and every 2 cycles thereafter until end of study (Day 1 of cycles 14, 16, 18, 20 and 24). However, when the patient is off the TKI with observation only in the adaptive arm, the patient needs to follow up every 28 days (+/- 7 days) for determination of starting a new cycle.

In each scheduled visit we will:

- Obtain vital signs.
- Record all concomitant medication use.
- Perform a comprehensive physical examination.
- Evaluate ECOG performance status.
- Obtain laboratory tests and urinary dipstick.
- Assess for AEs and SAEs.
- Assess compliance with the medication.
- Assess survival.

Thyroid panel evaluation

Thyroid panel will be assessed every 2 weeks during the first two cycles (Cycle 1 Day 15, Cycle 2 Day 1, Cycle 2 Day 15, and Cycle 3 Day 1). If the tumor marker (thyroglobulin in DTC patients; calcitonin or CEA in MTC patients) drops by $\geq 50\%$ from baseline (Cycle 1 Day 1) during the first two cycles (analysis of Cycle 3 Day 1 included), the patient will be randomized to receive either standard (continuous) or adaptive (intermittent) therapy. Patients randomized to

the standard therapy arm will then get Thyroid panel checked every 3 cycles (Day 1 of Cycle 6, 9, 12). Patients randomized to the adaptive therapy arm will get Thyroid panel checked every cycle (Day 1) during the first two years. After 24 months, patients in the adaptive therapy regimen who remain on TKI therapy will be given the choice to continue with the adaptive therapy regimen and monitoring of the thyroid panel in every cycle; or to convert to standard (continuous) regimen in which case thyroid panel evaluation will be checked every 3 cycles. In either case, all patients that continue to receive TKI therapy beyond 24 months will be treated off trial. Patients in which the tumor marker does not drop $\geq 50\%$ within the first two months of TKI therapy will be managed by the standard of care.

Diagnostic imaging

Diagnostic imaging of affected and suspected sites (CT and/or MRI) will be done at Day 1 of cycles 3, 6, 9, 12, 16, 20, 24 in all patients. Diagnostic imaging will continue to be done every 4 months thereafter while the patient remains on TKI therapy or as clinically indicated otherwise.

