8.4 REPORTING PROCEDURES

8.4.1 ADVERSE EVENT REPORTING

All AEs occurring prior to initiation of TKI therapy do not need to be reported.

All AEs occurring after first administration of TKI therapy (Lenvatinib, Sorafenib, Cabozantinib, or Vandetanib) and 30 days after last administration of TKIs will be considered as on treatment. All AEs will be collected and graded according to CTCAE v5.0 (Appendix 3), with the exception of Grade 1 laboratory abnormalities which will not be collected. All Grade 2 and above toxicities will be collected and documented by the investigator, but only Grade 3 toxicities deemed possibly, probably or definitely related to the study treatment will be reported on the appropriate CRFs/SAE reporting forms. Only SAEs will be reported to the PI. All AEs, including those persisting after end of study treatment must be followed up until they have resolved or have been sufficiently characterized or the principal investigator decides to not further pursue them.

Serious and non-serious AEs occurring later than 30 days after last administration of trial drugs will only be reported in case they are considered drug-related or trial (procedure) related.

Deaths (unless they are considered drug-related or trial related) will not be reported as SAE when they occur later than 30 days after last administration of the trial.

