10. STATISTICAL CONSIDERATIONS

10.1 STATISTICAL AND ANALYTICAL PLANS

This is a randomized phase II clinical trial with 2:1 randomization to adaptive therapy versus conventional therapy. The primary endpoint is time-to-discontinuation (TTD) of treatment, which is a "survival analysis"-type statistical comparison. We plan to enroll 24 patients on the adaptive therapy and 12 on the conventional therapy arm. Assuming uniform enrollment of patients for 2 years, with a minimum follow-up of 2 years, and a one-sided $\alpha = 0.20$, we will have 82% power to detect a hazard ratio of 0.50, assuming 12 and 24 month median TTD for the conventional and adaptive therapy groups. If the median TTD of the adaptive group is 20 months (HR=0.6), the power is 67%.

We anticipate that 20% of the patients will not have the $\geq 50\%$ drop in tumor markers needed for study randomization arm of the study. Thus, we anticipate recruiting ~45 patients to have 36 patients for randomization.

The ~9 patients enrolled to the trial not candidates for the randomization will be given conventional therapy as standard of care. As an exploratory analysis, and realizing that the sample sizes are small, we will compare their PFS rates with the 12 patients from the randomized portion of the trial who receive conventional therapy using the log-rank test.

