10.2 STATISTICAL HYPOTHESES

We hypothesize that we will prolong time to treatment discontinuation with the adaptive therapy regimen (**experimental group**) compared to the continuous therapy regimen (**control group**). Literature suggests that the median time to discontinuation with standard (continuous) therapy is 12 months. We hypothesize that the median time to discontinuation will increase to 24 months (Hazard ratio 0.50) with the adaptive therapy regimen. The power of the study to detect this difference is 82% for an alpha of 0.20.

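### The between-arm AE comparison has no denominator, time origin or analysis, and the only AE window defined would inflate adaptive-arm counts if time to discontinuation lengthens as hypothesized

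*Combined protocol and SAP*

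**What the plan says.** Section 8.1 places safety and toxicity among the primary endpoints and says the arms will be compared by "measuring incidence of AEs and SAEs and time to its developments in adaptive and conventional therapy arms". Sections 4.2.1 and 10.3.1 name only time to treatment discontinuation (TTD) as primary. Section 10 has methods for TTD, response, PFS, OS and biomarkers, and none for AEs.

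The one AE window is a reporting rule in 8.4.1: "All AEs occurring after first administration of TKI therapy (Lenvatinib, Sorafenib, Cabozantinib, or Vandetanib) and 30 days after last administration of TKIs" count as on treatment. The same section says that "only Grade 3 toxicities deemed possibly, probably or definitely related to the study treatment will be reported on the appropriate CRFs/SAE reporting forms".

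Randomization comes after treatment has begun. Section 4.1 randomizes a patient whose tumor marker falls by at least half "from the baseline level (before initiating TKI treatment) within the first two months of treatment", and until then everyone takes the same continuous TKI. Section 7.3.3 puts the first on-treatment marker check at Cycle 1 Day 15 and allows randomization up to the Cycle 3 Day 1 result. The shared run-in therefore lasts from about half a month to two months.

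On duration, 10.2 takes a 12-month median under continuous therapy and states: "We hypothesize that the median time to discontinuation will increase to 24 months". Section 10.1 also considers 20 months. Section 6.1.8 adds the cap: "Any treatment beyond the 24 months specified herein will be considered off protocol".

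**The concern.** Tolerability is half of the primary objective (Section 3), and fewer drug-associated toxicities are one of the two reasons 4.2.1 gives for expecting adaptive therapy to do better. TTD mixes intolerability with progression and disease-related death, so it does not isolate toxicity. The comparison in 8.1 is the planned between-arm look at toxicity itself.

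An analyst who falls back on the 8.4.1 window meets two problems. AEs from the run-in, when the arms are treated identically, dilute any difference. And if adaptive patients stay on protocol therapy longer, as the trial hopes, they are observed longer and accumulate more AEs for that reason alone. The crude comparison is then most misleading when the regimen succeeds on TTD. If durations turn out similar, only the run-in dilution remains.

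**Working it through.** **The plan's own figures.** The plan gives no number for the AE comparison, so I checked that its TTD assumptions are coherent before using them. With exponential TTD, 24 months of uniform accrual and 24 months of further follow-up, P(event) = 1 − (e^(−24λ) − e^(−48λ))/(24λ). This gives 10.4 conventional events, and 15.3 adaptive events at HR 0.50 or 16.9 at HR 0.60. Power = Φ(|ln HR|/√(1/d1 + 1/d2) − 0.842):

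- HR 0.50: Φ(0.693/0.402 − 0.842) = 81.1% (plan: 82%).
- HR 0.60: Φ(0.511/0.394 − 0.842) = 67.5% (plan: 67%).

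**Inputs from the plan.** Median TTD 12 (conventional) and m = 20 or 24 months (adaptive); treatment cap 24 months from first dose; window closing 30 days (1 month) after the end of therapy; run-in r = 0.5 to 2 months.

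**Assumptions.** Discontinuation is exponential from randomization. Adaptive patients count as in the window during TKI breaks. The adaptive AE rate is multiplied by k after randomization, with k = 1 (no difference) or 0.75 (a 25% cut; the plan gives no size). There are three AE shapes per month: A constant 0.10; B 0.20 for 3 months, then 0.05; C 0.30 for 3 months, then 0.03. Count ratios depend on the shape, not the level.

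**Constant rate, by hand.** Mean time on therapy after randomization is M(m) = (m/ln 2)(1 − 2^(−T/m)), T = 24 − r. AEs per patient are proportional to r + k(M + 1).

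- r = 2 (T = 22): M(12) = 12.45, M(20) = 15.39, M(24) = 16.28.
- No difference: m = 24 gives (2 + 17.28)/(2 + 13.45) = 1.248; m = 20 gives 18.39/15.45 = 1.190.
- 25% cut: m = 24 gives (2 + 0.75 × 17.28)/15.45 = 0.968; m = 20 gives (2 + 0.75 × 16.39)/15.45 = 0.925.

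**All shapes.** Adaptive/conventional AEs per patient, from first dose, by numerical integration:

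| r | m | k = 1: A, B, C | k = 0.75: A, B, C |
|---|---|---|---|
| 2 | 24 | 1.248, 1.157, 1.090 | 0.968, 0.949, 0.935 |
| 2 | 20 | 1.190, 1.120, 1.069 | 0.925, 0.922, 0.920 |
| 0.5 | 24 | 1.293, 1.185, 1.110 | 0.978, 0.911, 0.863 |
| 0.5 | 20 | 1.224, 1.142, 1.084 | 0.927, 0.878, 0.844 |

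**Which part does what (k = 0.75).** With equal durations (m = 12) the ratio is 0.759 to 0.868, which is run-in dilution alone. Starting the crude count at randomization while durations differ gives 0.822 to 0.977. Moving the origin is therefore not enough for a count.

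**Share of patients with at least one AE.** At constant rates of 0.02 to 0.5 per month over 24 months from randomization, a 25% cut shows as anything from 3% fewer to 7% more patients.

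**Plain patient-month rate.** With k = 1, r = 0.5, m = 24 and shape C, the ratio is 1.110/1.293 = 0.86. Later months carry fewer AEs, so the longer-treated arm looks better without being so.

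**Time to first AE.** Censoring at the end of the window, the large-sample Cox HR for a true 0.75 is 0.767 to 0.905 from first dose and 0.750 from randomization. From first dose it nears 1 when AEs are frequent: 0.91 to 0.995 at constant rates of 1 to 2 per month with a 1- to 2-month run-in.

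**The case against.** The best defence has four parts, and much of it stands.

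- **Incidence need not mean a crude count.** True. Section 8.1 does not say. The proportion of patients affected is equally natural, but unequal duration distorts it too, so the ambiguity does not protect the plan.
- **Section 8.1 already names time to AE, which copes with unequal follow-up.** True for duration, and onset time is collected (8.3). The origin is still missing, and the only one on offer is first dose.
- **Section 10.3.1 reads the primary endpoint at 12 months.** If AE counts were cut there, the same model gives 10% to 19% fewer for a 25% cut, and 2% to 13% more with no difference. The distortion is smaller, but nothing applies that cut-off to AEs.
- **Toxicity is visible elsewhere.** Reasons for removal are recorded (5.4.1, Section 9) and the monitoring committee reviews AEs (8.5). These help, but they are records and monitoring, not a between-arm analysis.

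A reader might also infer unequal AE capture, since Table 8 shows visits every three cycles for conventional patients. The documents do not settle this. Section 7.3.3 has participants seen every four weeks to cycle 12, Table 8 lists AE assessment as continuous, and its note l adds telephone reporting. No capture rate is given, so the effect cannot be sized.

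**Conclusion.** The gap is real and worth closing before data are seen. Using the 8.4.1 window with AEs per patient, and if the hypothesized TTD gain occurs, the adaptive arm would show about 19% to 29% more AEs with no true difference at a constant rate, and 7% to 18% more under the front-loaded shapes. An assumed 25% cut would show as about 2% to 8% fewer at a constant rate.

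Two stronger readings should be resisted. First, the 16% end does not follow from the medians alone. It needs AEs ten times as frequent in the first three months plus randomization at half a month. The plan's only support for early AEs is a remark about hand-foot syndrome (6.1.8.1). Second, the documents do not show that a toxicity benefit would be hidden whatever its size. With a 50% cut the same model gives crude counts 22% to 40% lower.

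The figures rest on the assumed AE shapes, effect size and exponential discontinuation, and on the TTD gain occurring. Only 8.1 calls this comparison primary, so it warrants a recommended change, not a threat to the trial's main result.

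**What to change.** In 8.1 and Section 10:

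1. Start the between-arm AE comparison at randomization and list run-in AEs separately.
2. For related Grade 3 or higher AEs and for SAEs, report time to first post-randomization AE, plus an exposure-aware incidence by time since randomization: either a mean cumulative count or a rate ratio with an approximate interval.
3. Define patients as at risk while on protocol therapy, TKI breaks included, plus 30 days after its permanent end.
4. Show discontinuations for intolerability alongside, because stopping for toxicity ends AE follow-up selectively.
5. Keep crude percentages as descriptive, and state in 8.4.1 that Grade 4 is included.

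The cost is a paragraph and modest programming. Onset, severity and relationship are already collected (8.3).

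The downside is imprecision. At an assumed 0.10 AEs per month with r = 2 and m = 24, a true ratio of 0.75 yields about 12 × 0.10 × 13.45 = 16.1 conventional and 24 × 0.075 × 17.28 = 31.1 adaptive AEs. The Poisson SE of the log ratio is √(1/16.1 + 1/31.1) = 0.31, so a 95% interval spans a factor of about 1.8 each way, roughly 0.41 to 1.37. Variation between patients widens it. Report an estimate, not a test. The change does not correct any difference in AE capture between arms.
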